### 10.3.2 Analysis Plan

To address our primary objective, we will conduct a Least absolute shrinkage and selection operator (Lasso) regression as our primary analysis. Specifically, our outcome, initial objective response, will be regressed on the change in each of the LEAD ultrasound tumor perfusion parameters after 3 weeks of treatment and relevant demographic and clinical characteristics. The measurement of LEAD ultrasound tumor perfusion parameters and the definition of their change are described in more detail below. We will not use selection techniques to choose variables. Rather, we will include all factors in our model jointly. We will evaluate the predictive ability of our model using area under the curve (AUC) and calculate a 95% confidence interval for the AUC. Since our sample size is too small to allow for separate training and testing datasets, we will utilize cross-validation techniques for evaluating predictive performance.

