#### Quantification of tumor perfusion parameters:

The following parameters are computed from the LEAD ultrasound measurements for each lesion:

- overall tumor perfusion: the integrated power within the tumor
- average red cell flux: the integrated power within the tumor normalized by tumor size
- tumor-to-background perfusion ratio: the ratio of the integrated power within the tumor to the integrated power in a same sized region in nearby healthy tissue.

Changes in tumor perfusion parameters after 3 weeks of treatment:

Defined as relative change in these parameters, i.e., difference between time points divided by value at time point 1, expressed as percentage. For determining the relative change in several lesions of the same patient, the average of the relative changes in the up to 5 individual lesions is calculated.

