### 10.4.2 Analysis Plan

To address our secondary objective, i.e., evaluating if there is an optimal ultrasound modality to predict initial objective response in arm 1, we will utilize the same analysis approach as outlined above for the primary analysis. Here, we will use change in tumor perfusion parameters at **6 weeks** as our independent variables and conduct two regression analyses: (1) using power Doppler measurements and (2) using LEAD ultrasound measurements. AUCs between the two models will be compared using the nonparametric approach of DeLong for correlated AUC curves. In addition, we will compare AUCs between these models to the predictive model for the primary analysis.

To assess if there is an optimal time point for predicting initial objective response in arm 1, we will conduct Lasso regression models using tumor perfusion parameters for each time point (treatment 'baseline', 3 weeks, 6 weeks) separately for each imaging modality using a similar approach as outlined above. Given the exploratory nature of these analyses, we will not adjust for multiple testing.

For each arm, we will conduct correlation analysis for change in perfusion parameters at 3 and 6 weeks and initial relative change in tumor burden (overall and per-lesion), initial overall response, best overall response, and PFS until 12 months after initiating treatment by calculating either the Pearson r or Spearman rank correlation, as appropriate. PFS is estimated using the Kaplan-Meier method and the Kaplan-Meier curves will be presented.

Selection of lesions for ultrasound exams:

The up to 5 lesions that were selected for ultrasound studies for the primary analysis are re-assessed 6 weeks (+/- 15 days) after start of treatment and each lesion is assessed with both LEAD and power Doppler ultrasound at all 3 time points (treatment 'baseline', 3 weeks, and 6 weeks after initiating treatment).

Quantification and change of tumor perfusion parameters: defined in the same way as for the primary analysis for both power Doppler and LEAD ultrasound.

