## **10.5 Sample Size**

Since this is an exploratory pilot study and we are not formally testing a specific research hypothesis, the sample size for each arm has been chosen based on practical considerations and estimated feasibility. However, for the primary analysis (arm 1), we consider a predictive model with a true AUC of at least 0.7 promising for predicting initial objective response. With 20 patients and assuming that 59% of patients have an objective response to treatment, a predictive model with a true AUC of at least 0.7 will have a margin of error of 0.14 so that the empirically determined AUC can range from 0.56 to 1.

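### DeLong's test in section 10.4.2 is applied to AUCs of lasso models cross-validated on the same 20 or so patients, so its standard error is too small and it finds modality differences too often

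*Protocol*

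**What the plan says.** For the optimal-modality objective, section 10.4.2 states "we will utilize the same analysis approach as outlined above for the primary analysis". The predictors become the 6-week changes, with one regression for power Doppler and one for LEAD, and the two AUCs are "compared using the nonparametric approach of DeLong for correlated AUC curves". The section also compares these models with the primary-analysis model, without naming a method.

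The approach carried over is set out in section 10.3.2. The plan is to "conduct a Least absolute shrinkage and selection operator (Lasso) regression as our primary analysis" and, because the sample is too small to split, "we will utilize cross-validation techniques for evaluating predictive performance". Each model uses three perfusion parameters together with "relevant demographic and clinical characteristics", whose number is not given.

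The number of folds, the penalty rule and a significance level for the comparison are not stated. Section 10.1 calls all secondary endpoints exploratory, and section 10.4.2 makes no multiplicity adjustment for its exploratory analyses.

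**The concern.** DeLong's formula estimates how far two AUCs would vary if new patients were drawn and the two markers stayed the same. In this plan the markers do not stay the same. Each score comes from a lasso refitted on most of the same patients, so a new sample would also change the selected coefficients and the shrinkage. The overlapping training sets make the out-of-fold scores dependent on one another. Neither source of variation is in the formula, so the standard error of the difference is too small and the p-value too low.

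Whether LEAD or power Doppler predicts better is the first secondary objective in section 1.2, and DeLong is the only method named for the comparison. If its error bars are too narrow, the report could present a chance difference between two equally good modalities as real.

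**Working it through.** **Plan's own figure.** The protocol gives no error rate or power for the DeLong comparison. Its only AUC precision figure is in section 10.5: "a true AUC of at least 0.7 will have a margin of error of 0.14". With A = 0.7, 12 responders and 8 non-responders, the Hanley-McNeil variance is [A(1−A) + 11(A/(2−A) − A²) + 7(2A²/(1+A) − A²)]/(12×8) = [0.210 + 0.533 + 0.605]/96 = 0.0140. The SE is 0.119 and the 95% margin 1.96 × 0.119 = 0.23, so 0.14 is not reproduced at the 95% level. That is a separate matter; nothing below depends on it.

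**Inputs from the protocol**
- N and response rate (section 10.5): "With 20 patients and assuming that 59% of patients have an objective response to treatment". 0.59 × 20 = 11.8, taken as 12 against 8.
- Three parameters per modality (section 10.3.2, quantification of perfusion parameters; section 10.4.2 applies the same definition to power Doppler).
- Lasso with cross-validation (section 10.3.2).

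**Assumptions, because the protocol is silent**
- 5-fold, 10-fold or leave-one-out.
- Penalty fixed, or tuned by inner 5-fold cross-validation.
- 0 or 3 shared covariates.
- Correlation between modalities 0, 0.5 or 0.8; between parameters within a modality 0.5.
- DeLong applied to pooled out-of-fold scores, two-sided 5%.

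**Method.** Simulate trials in which both modalities have the same true predictive ability, so every rejection is false. Refit the lasso in each fold, pool the predictions and apply DeLong (200 to 1,500 trials per scenario). The Monte Carlo standard error of a rate near 15% lies between √(0.15×0.85/1500) = 0.9 and √(0.15×0.85/200) = 2.5 percentage points.

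**Results at modality correlation 0.5 and AUC 0.70 per parameter**

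| Score given to DeLong | True SD of difference | Mean DeLong SE | Rejection |
|---|---|---|---|
| Single unfitted marker | – | – | 4.9% |
| 5-fold, fixed penalty, no covariates | 0.199 | 0.148 | 14.7% |
| 10-fold, fixed penalty, no covariates | – | – | 14.9% |
| 5-fold, tuned penalty, no covariates | 0.216 | 0.141 | 19.3% |
| 5-fold, fixed penalty, 3 covariates | – | – | 11.5% |
| 5-fold, tuned penalty, 3 covariates | 0.191 | 0.132 | 14.7% |
| 10-fold, tuned penalty, no covariates | 0.230 | 0.131 | 23.0% |
| Leave-one-out, fixed penalty, no covariates | 0.217 | 0.146 | 18.5% |
| Leave-one-out, tuned penalty, no covariates | 0.371 | 0.131 | 45.5% |

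**Shortfall in the SE.** In the 5-fold, fixed-penalty, no-covariate row it is 1 − 0.148/0.199 = 26%. With the tuned penalty it is 1 − 0.141/0.216 = 35%.

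**Consistency check.** If the difference is roughly normal, the rejection rate should be 2[1 − Φ(1.96 × SE/SD)]. For the fixed-penalty row, 1.96 × 0.148/0.199 = 1.46, which gives 14.5% against the simulated 14.7%. For the tuned row, 1.96 × 0.141/0.216 = 1.28, which gives 20% against 19.3%. The SE shortfall explains the excess.

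**Range over all scenarios.** Rejection ran from 5.7% to 29% for 5- or 10-fold (5.7/5 = 1.1 times nominal; 29/5 = 5.8 times) and from 13% to 53% for leave-one-out (2.6 to 10.6 times). The lowest values came with highly correlated modalities, shared covariates and no signal; 5.7% cannot be told apart from 5% within simulation error.

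**Effect of sample size.** With 5-fold and a fixed penalty, rejection falls to 8.7% at N = 100 and 6.0% at N = 200.

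**Check of the remedy.** The modality labels were swapped within patient and the whole lasso and cross-validation rerun (5-fold, fixed penalty, correlation 0.5, 300 trials, 99 permutations). Rejection was 5.3% with no signal and 5.7% at AUC 0.70 per parameter. DeLong on the same data rejected 20.0% and 14.3%.

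**The case against.** The best case for leaving the text alone is that nothing depends on this p-value. Section 10.1 calls the secondary endpoints hypothesis-generating, and section 10.5 says no specific hypothesis is formally tested. No level is attached to the comparison, so the 5% benchmark is mine. Section 10.7 picks the model with the best AUC, a point-estimate rule that a narrow standard error cannot change, and then requires validation in an independent cohort. All of this stands and limits the consequence. It does not make the standard error right: exploratory status excuses low power and unadjusted multiplicity, not a variance formula that leaves out the fitting.

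Three stronger readings are tempting, and the protocol does not support them.
- A reader might infer that DeLong decides which modality goes forward. Section 10.7 does not use it. That section mentions equivalent AUCs without defining them, does not tie them to DeLong, and leads from there only to additional analyses.
- A reader might take a fixed multiple, such as three, as a property of the plan. Folds, penalty, covariates and modality correlation are all open, and the multiple moves with each of them.
- A reader might compare the spread of a single cross-validated AUC with its own DeLong SE. One such simulation gave 0.16 against 0.10, a 37% shortfall. The test uses the SE of the difference between two AUCs, so that comparison does not measure this defect.

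The permutation test has limits too. It tests whether the two modalities are exchangeable, which is stricter than equal AUC. It also has little power at this size: about 21% in one simulation where the mean cross-validated AUCs were 0.70 and 0.45.

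**Conclusion.** The concern holds in limited form. The protocol names a specific test for a specific kind of score, and the two do not fit. In the central fixed-penalty setting the standard error of the AUC difference is about a quarter too small. Most 5- or 10-fold settings at modality correlation 0.5 and AUC 0.70 per parameter gave 11.5% to 19.3% false differences, or 2.3 to 3.9 times a nominal 5%; 10-fold with a tuned penalty gave 23.0%. The wider range is about 1.1 to 6 times, and more with leave-one-out. These sizes rest on the simulation assumptions listed above, including pooled out-of-fold scores and a two-sided 5% level.

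What is at risk is the reported modality comparison, an exploratory secondary result. The primary analysis is not shown to be affected: section 10.3.2 does not name the method for its confidence interval, so no conclusion about that interval follows. The point merits a wording change before the analysis is run.

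**What to change.** In section 10.4.2, replace DeLong in one of two ways.

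1. **Paired permutation test.** Take patients with both modalities at baseline and week 6, and standardise each parameter within modality. Exchange the LEAD and power Doppler parameter sets at random within patient, leaving outcome and covariates in place. Rerun the whole procedure, including penalty choice and cross-validation, and compare the observed AUC difference with the resulting distribution. Fix the folds, penalty rule and number of permutations before the data are analysed.
2. **Descriptive report.** Give both cross-validated AUCs and their difference, without a DeLong p-value. With the power available at n = 20, this is at least as defensible.

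Treat the comparison with the primary-analysis model in the same way, since those AUCs are produced by the same procedure.

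Do not substitute a naive patient-level bootstrap. Copies of one patient can then fall in both training and test folds: in a no-signal simulation (80 datasets, 60 resamples each) the mean cross-validated AUC rose from 0.43 to 0.57 on resampling, so the interval would be centred in the wrong place.

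The cost is a change of analysis wording and slightly more computing, with no new data. The drawbacks are low power and a null hypothesis of exchangeable modalities, which the report should state.

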## PROTOCOL SYNOPSIS

TITLE	Early therapeutic monitoring of response to therapy with serial ultrasound in metastatic RCC
STUDY PHASE	Pilot
INDICATION	Metastatic Renal Cell Carcinoma (mRCC)
INVESTIGATIONAL PRODUCT OR PROCEDURE	Study of power Doppler ultrasound for early detection of therapeutic response after initiating therapy with: arm 1: tyrosine kinase (TKI) inhibitor plus immune checkpoint inhibitor (ICI) arm 2: non-ICI therapy (e.g., TKI monotherapy, combination of TKI with other kinase inhibitor, localized tumor therapy such as radiation, chemo- or radioembolization)
PRIMARY OBJECTIVE(S)	To assess whether changes in quantitative tumor perfusion parameters after 3 weeks of treatment, as measured by LEAD ultrasound, can predict initial objective response, defined by current standard-of-care, to therapy at 12 weeks after start of treatment
SECONDARY OBJECTIVE(S)	To evaluate if there is an optimal ultrasound imaging modality (power Doppler or LEAD ultrasound) or optimal time point to predict initial objective response, to assess the correlation of tumor perfusion parameters with change in overall tumor burden, change in diameter on a per-lesion basis and with 12-month progression-free survival (PFS).
STUDY PROCEDURE SUMMARY	power Doppler and LEAD ultrasound of subjects taking targeted therapy medication, measured at treatment 'baseline', 3-4 weeks, and 6-8 weeks after initiating treatment
SAMPLE SIZE	arm 1: 20 subjects arm 2: up to 10 subjects
STATISTICAL CONSIDERATIONS	We will evaluate the predictive ability of each model using area under the curve (AUC). For this pilot study, assuming that 59% of patients in arm 1 have an objective response to treatment, a predictive model with a true AUC of 0.7 will have a margin of error of 0.14 so that the estimated AUC can range from 0.56 to 0.84.

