### 1.2 Secondary Objectives

Our secondary objectives are to evaluate in arm 1, if there is an optimal ultrasound imaging modality (power Doppler or LEAD ultrasound), or optimal time point to predict initial objective response. We will assess how well 1) changes in tumor perfusion parameters 6 weeks after start of treatment by imaging modality or 2) tumor perfusion parameters at a single time point (treatment 'baseline', 3 weeks, or 6 weeks after start of treatment), predict initial objective response (at 12 weeks) per RECIST v1.1.

Additional exploratory objectives in both arms are to assess the correlation of tumor perfusion parameters with change in overall tumor burden (defined as sum of the longest diameters of all measurable lesions defined by RECIST v1.1) 12 weeks after start of treatment, with change in diameter on a per-lesion basis (correlation between perfusion parameters of a single lesion with change in diameter of that lesion), and with 12-month progression-free survival (PFS).

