##### Arm 2: Non-ICI Treatment

- planned to be treated with non-ICI therapy\*\*

\*\* including, but not limited to: TKI monotherapy, other kinase inhibitors (e.g., mTOR inhibitors) alone or in combination with TKIs, localized tumor therapy such as radiation, chemo- or radioembolization

Subjects may participate in the study more than once at the discretion of the Protocol Director, for example, if they receive different lines of treatment that all qualify for the study.

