## 9.2 Secondary Outcome Measures

Secondary endpoints are:

- 1) **initial relative change in tumor burden** (continuous): defined as relative change (i.e., difference between time points divided by value at time point 1, expressed as percentage) in the sum of all tumor diameters between treatment 'baseline' and first on-treatment response evaluation 8-16 weeks after start of treatment, using RECIST v1.1 for tumor diameter measurements, expressed as mean +/- standard deviation and median with interquartile range
- 2) **initial lesion response** (continuous): defined as the relative change in tumor diameter of a single lesion between treatment 'baseline' and first on-treatment response evaluation 8-16 weeks after start of treatment, using RECIST v1.1 for tumor diameter measurements, expressed as mean +/- standard deviation and median with interquartile range.
- 3) **12-month progression-free survival (PFS)** (yes/no): defined as not having experienced any PD per RECIST v1.1 within the first 12 months after initiating treatment (day 1 will be treatment start date), as a number and proportion without dispersion.

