#### Selection of lesions for LEAD ultrasound exams:

Before the first ultrasound exam, the treating medical oncologist, a Protocol Director, or a designated radiologist selects up to 5 lesions per patient (target lesions per RECIST v1.1). At the treatment 'baseline' LEAD ultrasound exam (up to 28 days prior to start of treatment), perfusion of these 5 lesions is measured. Additional lesions may be assessed at the discretion of the investigators, so that in the end up to 5 lesions are selected for repeat ultrasound exams that in the opinion of the investigators lend themselves to reproducible tumor perfusion measurements. LEAD ultrasound tumor perfusion measurements of the up to 5 lesions that were selected for ultrasound studies at the treatment 'baseline' exam are performed again 3 weeks (+/- 8 days) after start of treatment.

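### The per-lesion correlations use plain Pearson or Spearman coefficients, with nothing to account for several lesions coming from one patient

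*Protocol*

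**What the plan says.** Section 1.2 defines the per-lesion objective, in both arms, as the "correlation between perfusion parameters of a single lesion with change in diameter of that lesion". Section 9.2 makes the matching endpoint continuous, with one value per lesion: "the relative change in tumor diameter of a single lesion between treatment" baseline and the first on-treatment evaluation.

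Section 10.3.2 allows several lesions per patient; the selecting clinician "selects up to 5 lesions per patient (target lesions per RECIST v1.1"). Section 10.4.2 carries the same lesions into the secondary analyses. It correlates perfusion change at 3 and 6 weeks with "initial relative change in tumor burden (overall and per-lesion"), among other outcomes, separately for each arm and "by calculating either the Pearson r or Spearman rank correlation, as appropriate".

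The only handling of several lesions in one patient is in section 10.3.2, where "the average of the relative changes in the up to 5 individual lesions is calculated". That gives one value per patient. No section names a patient effect, a repeated-measures correlation, a cluster-based interval or a rule of one lesion per patient.

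**The concern.** Lesions in one patient share treatment, tumour biology, scanning session and body habitus, so their perfusion and diameter changes are likely to be correlated. An ordinary coefficient over all lesions has two consequences.

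- **Interpretation.** A pooled coefficient can be large because patients who respond differ from those who do not, even if perfusion says nothing about which lesion within a patient shrinks. The patient-level correlation in the same section already addresses the between-patient question. What a per-lesion analysis can add is the within-patient part, and the pooled figure does not isolate it. A patient with 5 lesions also counts five times as much as a patient with one.
- **Precision.** Any p-value or interval that takes the number of lesions as the sample size is too optimistic when lesions within a patient are alike.

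At stake is which hypothesis the pilot passes on: that ultrasound perfusion works lesion by lesion, or only that it separates patients.

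**Working it through.** **Inputs from the protocol.** Numbers of patients: "arm 1: 20 subjects arm 2: up to 10 subjects" (synopsis). Lesions per patient: 1 (the minimum in section 3.1) to 5 (section 10.3.2). Statistic: Pearson or Spearman (section 10.4.2). The protocol states no power or precision for this correlation, so there is no figure to reproduce.

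**Assumed inputs.** The protocol gives no ICC. It is taken as equal for perfusion change and diameter change and varied from 0 to 0.7. Patient and lesion effects are bivariate normal.

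**Step 1: what the pooled coefficient measures.** With equal ICCs,

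pooled r ≈ ICC × r_between + (1 − ICC) × r_within.

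At ICC 0.5, with 20 patients and 5 lesions each:

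| r_between | r_within | Formula | Simulated mean r |
|---|---|---|---|
| 0.8 | 0 | 0.5 × 0.8 + 0.5 × 0 = 0.40 | 0.38 |
| 0 | 0.8 | 0.5 × 0 + 0.5 × 0.8 = 0.40 | 0.41 |
| −0.5 | +0.5 | 0.5 × (−0.5) + 0.5 × 0.5 = 0 | 0.02 |

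The first two rows describe opposite situations and give nearly the same coefficient. In the third, two real associations cancel.

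**Step 2: effective number of pairs.** With no association and m lesions per patient, the design effect is 1 + (m − 1) × ICC_x × ICC_y. For m = 5:

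| ICC (both) | Design effect | 20 × 5 = 100 pairs are worth | 10 × 5 = 50 pairs are worth |
|---|---|---|---|
| 0.1 | 1 + 4 × 0.01 = 1.04 | 96 | 48 |
| 0.3 | 1 + 4 × 0.09 = 1.36 | 74 | 37 |
| 0.5 | 1 + 4 × 0.25 = 2.00 | 50 | 25 |
| 0.7 | 1 + 4 × 0.49 = 2.96 | 34 | 17 |

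Near r = 0, the 95% half-width from the Fisher transformation is tanh(1.96/√(n − 3)). It is 0.20 for 100 independent pairs, 0.28 for 50 and 0.34 for 34.

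At ICC 0.6 the design effect is 1 + 4 × 0.36 = 2.44. The SD of r over 100 pairs is then about 0.10 × √2.44 = 0.156. Simulation gives 0.155, against about 0.10 if the pairs were independent.

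**Step 3: false-positive rate of the ordinary test at nominal 5%.** Simulated with zero true association, Pearson, 10,000 runs per cell:

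| Setting | ICC 0 | 0.1 | 0.3 | 0.5 | 0.7 |
|---|---|---|---|---|---|
| 20 patients, 5 lesions each | 5.0% | 5.7% | 9.5% | 16.6% | 25.8% |
| 20 patients, 1 to 5 lesions spread evenly (60 lesions) | 4.6% | 5.3% | 7.4% | 12.0% | 19.4% |
| 10 patients, 5 lesions each | 5.2% | 5.6% | 9.6% | 15.8% | 26.7% |

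Spearman is nearly the same (24.9% in the first row at ICC 0.7). With 20 patients and 3 lesions each, the rate is about 7% at ICC 0.3, 9% at 0.4, 11% at 0.5 and 14% at 0.6. With 5 lesions each it is about 21% at ICC 0.6. Separate simulation runs agree to within about one percentage point.

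**The case against.** The strongest reply has five parts.

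1. **The protocol does not say that lesions are pooled.** Section 10.4.1 describes the correlation data sets in terms of patients, and the interval method could be set in an analysis plan that is not shown. This stands in part: pooling is an inference. But the protocol itself fixes the unit (a lesion) and the coefficient, and the choice left open is only between Pearson and Spearman, neither of which handles clustering. Applying the averaging rule instead would remove the per-lesion analysis.
2. **No p-value, interval or significance level is attached to these correlations.** This stands. A reader might infer from Step 3 that the plan contains a test with an inflated error rate. It does not; the rates apply only if such inference is reported on the lesion count.
3. **The objective does not ask for a within-patient association.** This also stands. A reader might infer that the plan targets the wrong estimand, but section 1.2 can be read as asking for a marginal lesion-level correlation, which a pooled coefficient estimates in a fashion. The defensible point is narrower: that coefficient cannot separate the two sources of association.
4. **The size depends on unknowns.** This is correct. Inflation is slight at ICC 0.1, and it depends on the product of the two ICCs. With ICCs of 0.6 and 0.2 and 3 lesions, the design effect is 1 + 2 × 0.12 = 1.24, or about 8% error by normal approximation. A reader might also infer that arm 2 will be shown as 50 observations. That is an upper bound: eligibility needs only one suitable lesion, arm 2 may have fewer than 10 patients, and section 9.1.1 lets the radiologist measure lesions other than those scanned.
5. **Little depends on the result.** Section 10.1 calls all secondary endpoints hypothesis-generating, and the criterion in section 10.7 uses only the AUC. This limits the importance of the point but does not answer it.

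**Conclusion.** The point holds as a fault in a fixed method, with limited impact. The mixing of the two associations does not depend on any p-value; it matters whenever between-patient and within-patient associations differ.

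The loss of precision is conditional on inference that uses the lesion count, on equal ICCs in both variables and on the number of lesions actually paired. Within those assumptions it runs from negligible at ICC 0.1 to a false-positive rate of roughly three to four times nominal at ICC 0.6 (14/5 = 2.8 to 21/5 = 4.2). Arm 2 with 5 lesions each behaves like arm 1 with 5 lesions each.

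Repeat enrolment could add dependence that these figures leave out, since "Subjects may participate in the study more than once at the discretion of the Protocol Director". The primary analysis and the decision on a follow-up study are not affected.

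**What to change.** State in section 10.4.2 that the per-lesion analysis accounts for patient. A suitable form is a mixed model of lesion diameter change on lesion perfusion change, with a patient random intercept and with perfusion change split into the patient mean and the lesion's deviation from it. An alternative is a repeated-measures correlation among patients with at least 2 lesions. Take intervals by resampling patients, not lesions, keeping repeat enrolments of one person together, and report the numbers of patients and lesions with every estimate.

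The change needs a sentence or two and no new data, because section 8.2 already requires lesion identity, perfusion parameters and diameters on the case report form. It has three costs. Intervals become wider. Patients with a single lesion contribute nothing to the within-patient estimate. With up to 10 patients in arm 2, both the mixed model and the patient bootstrap are unstable, so per-lesion results there should be descriptive only.
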